6.2 RESPONSE CRITERIA

6.2.1 Determination of Immunologic Response

6.2.1.1 Local Immunologic Response

The primary endpoint of this study will be to examine the ability of the vaccine to induce a local T-cell response in the prostate. CD4 and CD8 cell infiltrates will be examined in the peri-tumoral region of the prostate biopsy specimens as well as in the prostate specimen itself. Utilizing computer automated staining analysis, density of cell infiltrate will be calculated and the pre and post-vaccine values will be compared to determine response to vaccine.

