5.1.1 Immune cell infiltrate

Slides made from prostate biopsy specimens (collected at baseline) and prostatectomy specimens (collected at surgery performed after last dose of vaccine) will be stained for CD4 and CD8 cells and digitized for analysis of immune cell infiltrate. Other markers such as CD4/FoxP3 may also be stained for further correlative studies. These studies will be performed by the Laboratory of

Tumor Immunology and Biology. At a minimum, 5 slides from one biopsy core confirmed to contain cancer will be needed for baseline quantification. Attempts will be made based on anatomic location notation or when available, MRI based location, to correlate biopsy location with pathologic location on prostatectomy specimens. When feasible, quantitation will be performed in triplicate. Quantitation will be reported as number of stained cells per micron squared of surface area. Wilcoxon matched pair signed rank test, Friedman test with Dunn's multiple comparisons, or alternative statistical models will be used as appropriate. Aperio ScanScope digital scanner systems with Aperio ImageScope software algorithms will be used. Manual quantitation will be performed in case of software malfunction. Isotype antibodies negative controls will be included in all runs. Tonsil or lymph node tissue will be positive control for CD4 and CD8. Slides will be developed with primary and secondary antibodies per manufacturer specifications for visualization of cells.

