8 STATISTICAL SECTION

The primary objective of this trial is to determine the effect of prostate cancer vaccine on CD4 and CD8 cell infiltrate staining.

The primary endpoints will be the changes from baseline to after surgery of the CD4 and CD8 cell infiltrates. The fold change from baseline to post surgery biopsy will be the primary endpoint for each measure. With two primary parameters to be measured with respect to a change at one time point, the sample size will be selected to allow each test to be performed using a 0.025 two-tailed significance level, in order to allow the overall set of two tests to be very conservatively performed as if at an overall 0.05 level using a Bonferroni adjustment. With 24 total patients with full measurements on both parameters at baseline and post-surgery, there would be 80% power to detect a change from baseline equal to 0.67 standard deviations of the change (0.67 effect size) using a two-tailed 0.025 level paired t-test. In practice, instead of requiring that each test achieve a 0.025 level in order to be declared significant, if appropriate to do so, a less overly stringent Hochberg adjustment may be performed. In addition, if the differences from baseline to post-surgery are not normally distributed (that is, if $p < 0.05$ by a Shapiro Wilks test) then a Wilcoxon signed rank test will be performed instead.

It is anticipated that 1-2 patients per month may enroll on this trial. Thus, it is expected that up to 2 years may be required to enroll 24 evaluable patients. In order to allow for a small number of inevaluable patients, the accrual ceiling for the trial will be set at 27 patients.

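### Baseline infiltrate density may rest on one biopsy core while the prostatectomy compartment and area are not fixed, so the single-arm fold change can be biased

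*Combined protocol and SAP*

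**What the plan says.** Section 8 gives the aim: "The primary objective of this trial is to determine the effect of prostate cancer vaccine on CD4 and CD8 cell infiltrate staining". It sets the scale, "The fold change from baseline to post surgery biopsy will be the primary endpoint for each measure", and sizes the trial at 24 evaluable patients for 80% power at 0.67 SD of the change, "using a two-tailed 0.025 level paired t-test". A Wilcoxon signed rank test replaces the t-test if Shapiro-Wilk gives p < 0.05.

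Section 6.2.1.1 describes the tissue: infiltrates "will be examined in the peri-tumoral region of the prostate biopsy specimens as well as in the prostate specimen itself". Peri-tumoral is attached to the biopsy; whether it also governs the surgical specimen is not clear.

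Section 5.1.1 sets the baseline minimum: "At a minimum, 5 slides from one biopsy core confirmed to contain cancer will be needed for baseline quantification". It gives no corresponding compartment, field count or area for the prostatectomy. It does contain three safeguards:

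- Attempts will be made "to correlate biopsy location with pathologic location on prostatectomy specimens".
- "When feasible, quantitation will be performed in triplicate". It does not say whether this means fields, slides or repeat reads, or whether it applies at both time points.
- "Quantitation will be reported as number of stained cells per micron squared of surface area", so the measure is normalised for the amount of tissue.

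Section 3.1 describes one treated group with no control.

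**The concern.** The biopsy is the only reference for the vaccine effect. If biopsy and prostatectomy are sampled differently, the difference in sampling enters the primary endpoint, and no control arm would reveal it.

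Two mechanisms are possible. First, a small core gives a more variable density than a large surgical area. With that density in the denominator, the expected ratio exceeds 1 even when nothing has changed, and the log ratio shifts too if the noise is unequal. Second, if the compartments differ, the two densities may differ for reasons unrelated to vaccination. That could create a false rise or hide a real one.

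**Working it through.** **The plan's own figure.** n = 24, effect 0.67 SD, two-sided 0.025, paired t-test. The noncentrality is 0.67 × √24 = 3.28 and the critical value on 23 df is 2.398. Power is 80.5%, so the stated 80% reproduces. It presumes that the mean change is zero when the vaccine does nothing.

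**Unequal noise, same compartment, no vaccine effect.** The documents give no variance, so the log-SDs are assumptions. Let baseline density B be lognormal with log-SD sb and post density P lognormal with log-SD sp, both with mean 1. Then:

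- mean raw fold change: E[P/B] = exp(sb²)
- geometric mean fold change: exp((sb² − sp²)/2)
- mean difference: E[P − B] = 0

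At sb = 0.6 and sp = 0.3 these are exp(0.36) = 1.43, exp(0.135) = 1.14, and 0. The 1.43 does not contain sp: it comes from using a ratio and would be the same with matched sampling. The 1.14 is the part due to unequal noise.

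Simulated rejection rates under this null (24 patients per trial, several thousand trials per row, Shapiro-Wilk then t-test or Wilcoxon, nominal 2.5% two-sided per marker; a range is given where repeat runs differed):

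| Core / surgical log-SD | Raw fold | Log ratio | Difference |
|---|---|---|---|
| 0.3 / 0.15 | 10% | 5% | 3–4% |
| 0.4 / 0.3 | 9–10% | 3% | 3% |
| 0.6 / 0.3 | 25% | 10% | 5% |
| 0.8 / 0.4 | 38% | 16% | 6–7% |
| 0.6 / 0.6 (equal) | 6–7% | 2–2.5% | 2–2.5% |

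On the raw fold change, nearly all rejections are false rises.

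A second set-up agrees. It takes one region before and ten after, with an assumed single-region CV of 0.3, 0.6 or 1.0. False rises, against 1.25% nominal in that tail, are:

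- raw fold: 9.7%, 27.8%, 49.2%
- log fold: 4.6%, 11.6%, 23.6%
- difference: 2.2%, 4.4%, 9.0%

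With three regions before and ten after, the raw-fold rates fall to 4.8%, 10.9% and 17.9%.

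**Compartment mismatch.** Add a pure sampling offset, in SDs of the change, to a true null. Offsets of +0.1, +0.2, +0.3 and +0.5 SD give a false significant rise in 3.8%, 9.4%, 19.7% and 53.0% of trials. Negative offsets give false falls at the same rates. An offset of −0.3 SD leaves 0.67 − 0.3 = 0.37 SD of a true effect and cuts power from 80.5% to 29.9%. In the one-before, ten-after set-up at CV 0.6, a post region that is truly 30% less dense gives 0% false rises and 14.6% false falls on the raw fold.

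**The remedy.** Use k core-sized surgical regions with averaged log densities. The mean log ratio is 0 and its variance is sb²(1 + 1/k). For sb = 0.6 and k = 4, the SD is √(0.36 × 1.25) = 0.67. The unmatched 0.6/0.3 case has √(0.36 + 0.09) = 0.67, so no precision is lost if the regions are independent. Simulated type I error on the log ratio is about 2.5% to 2.8%. Leaving the endpoint as a raw fold still gives about 6% or more.

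**The case against.** A reader might infer that unequal sampling by itself must produce an apparent rise. The documents do not support that. Density is reported per unit area, and sampling more tissue does not raise its average. The upward push needs a variable baseline density, analysis as a ratio, and equal true density in the two sampled areas. The documents do not say which area is denser, and a mismatch can reverse the sign.

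A reader might also charge the whole 25% to unequal sampling. Equal noise already gives 6% to 7% on the raw fold, so part of it belongs to the ratio scale.

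Other points count for the plan:

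- One core is a minimum, not the rule for every patient.
- Peri-tumoral can be read as covering both specimens.
- If triplicate means three independent baseline regions, which is not stated, the log-SD of 0.6 falls to √ln(1 + (exp(0.36) − 1)/3) = 0.37. Against 0.3, the rates are then about 7.9% (fold), 3.3% (log) and 3.0% (difference).
- Section 8 refers its power and normality check to changes or differences, so the test might be run on differences, where inflation is smallest.

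These points reduce the likely size but do not close the gap. Matching and triplicate are conditional, neither fixes compartment or area, and Section 8 names the fold change as primary. Normalising per unit area corrects the mean density, not its noise.

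**Conclusion.** The concern holds in conditional form. The plan does not fix the compartment or sampled area for the prostatectomy, allows a one-core baseline, and analyses a fold change without a control. Following it as written can bias the primary result. Given equal true density, noisier baseline sampling inflates the fold change; compartment mismatch has no fixed direction and can also mask a real effect.

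Across the unequal-noise scenarios in the table, type I error at a nominal 2.5% runs from about 9% to 38% on the raw fold, 3% to 16% on the log ratio and 3% to 7% on the difference. These figures rest on assumed lognormal variability and show a range, not an estimate for this trial. Moving to logs alone does not suffice while sampling is unequal, and matched sampling alone does not suffice while the fold stays raw. Both changes are needed.

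**What to change.** - **Sections 5.1.1 and 6.2.1.1:** require the same named compartment, peri-tumoral, in both specimens.
- **Section 5.1.1:** on the digitised prostatectomy slides, place several core-sized regions at the mapped biopsy site, chosen without sight of the CD4/CD8 staining. Compute the log density in each and average the logs. State what triplicate means and apply it at both time points.
- **Section 8:** define the primary endpoint for each marker as the log fold change, and apply the normality check and test to that quantity. The sample size of 24 for 0.67 SD is unchanged, with the SD now that of the log fold change.
- **Sensitivity analysis:** flag patients whose biopsy site cannot be mapped and repeat the analysis without them.

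The cost is protocol wording and some extra image-analysis time on slides already planned for scanning, with no new tissue or procedure. Neighbouring regions may be correlated; that would reduce the gain in precision but would not bring back the bias.

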6.2.1.2 Systemic Immunologic Response

In order to evaluate the potency of clinical vaccines to induce a systemic response, assays that determine an antigen-specific T lymphocyte response to vaccines have been employed. Immune response T-cell assays (such as the ELISPOT assay) have been used successfully in numerous vaccine trials. The ability to detect single cells that produce interferon gamma has led to specificities of 80-95%. ELISPOT has very good reproducibility both when the same sample is tested at two time points and when an individual is tested at different time points. We have also seen minimal variation in the flu-specific ELISPOT in patients when tested at time points about 84 days apart. Utilizing these immune response assays, the change in PSA-specific T-cell response from baseline to after the last vaccination will be considered for evidence of an immunologic response to the vaccine.

6.3 TOXICITY CRITERIA

6.3.1 CTCAE

The following adverse event management guidelines are intended to ensure the safety of each patient while on the study. The descriptions and grading scales found in the revised NCI Common Terminology Criteria for Adverse Events (CTCAE) version 4.0 will be utilized for AE reporting. All appropriate treatment areas should have access to a copy of the CTCAE version 4.0. A copy of the CTCAE version 4.0 can be downloaded from the CTEP web site (http://ctep.cancer.gov/protocolDevelopment/electronic_applications/ctc.htm#ctc_40).

6.3.2 Toxicity Grading for Vaccinia Toxicity

- Grade 1: Generalized vaccinia extending no more than 10 cm from the vaccination site (i.e., limited to the upper arm).
- Grade 2: Any autoinoculation syndrome that resolves without sequelae; generalized vaccinia extending more than 10 cm from the vaccination site.
- Grade 3: Any toxicity that is between grades 2 and 4.
- Grade 4: Autoinoculation syndrome with sequelae (e.g., blindness); post-vaccinia encephalitis; vaccinia gangrenosum; eczema gangrenosum; Stevens-Johnson syndrome.
- Grade 5: Death

7 SAFETY REPORTING REQUIREMENTS/DATA AND SAFETY MONITORING PLAN

7.1 DEFINITIONS

7.1.1 Adverse Event

An adverse event is defined as any reaction, side effect, or untoward event that occurs during the course of the clinical trial associated with the use of a drug in humans, whether or not the event is considered related to the treatment or clinically significant. For this study, AEs will include events reported by the patient, as well as clinically significant abnormal findings on physical examination or laboratory evaluation. A new illness, symptom, sign or clinically significant laboratory abnormality or worsening of a pre-existing condition or abnormality is considered an AE. All AEs must be recorded on the AE case report form unless otherwise noted above in Section 6.1.

All AEs, including clinically significant abnormal findings on laboratory evaluations, regardless of severity, will be followed until return to baseline or stabilization of event. Serious adverse events that occur more than 30 days after the last administration of investigational agent/intervention and have an attribution of at least possibly related to the agent/intervention should be recorded and reported as per sections 7.2, 7.3, 7.4.

An abnormal laboratory value will be considered an AE if the laboratory abnormality is characterized by any of the following:

- Results in discontinuation from the study
- Is associated with clinical signs or symptoms
- Requires treatment or any other therapeutic intervention
- Is associated with death or another serious adverse event, including hospitalization.
- Is judged by the Investigator to be of significant clinical impact
- If any abnormal laboratory result is considered clinically significant, the investigator will provide details about the action taken with respect to the test drug and about the patient's outcome.

7.1.2 Suspected adverse reaction

Suspected adverse reaction means any adverse event for which there is a reasonable possibility that the drug caused the adverse event. For the purposes of IND safety reporting, 'reasonable possibility' means there is evidence to suggest a causal relationship between the drug and the adverse event. A suspected adverse reaction implies a lesser degree of certainty about causality than adverse reaction, which means any adverse event caused by a drug.

7.1.3 Unexpected adverse reaction

An adverse event or suspected adverse reaction is considered "unexpected" if it is not listed in the investigator brochure or is not listed at the specificity or severity that has been observed; or, if an investigator brochure is not required or available, is not consistent with the risk information described in the general investigational plan or elsewhere in the current application. "Unexpected", also refers to adverse events or suspected adverse reactions that are mentioned in the investigator brochure as occurring with a class of drugs or as anticipated from the pharmacological properties of the drug, but are not specifically mentioned as occurring with the particular drug under investigation.

7.1.4 Serious

An Unanticipated Problem or Protocol Deviation is serious if it meets the definition of a Serious Adverse Event or if it compromises the safety, welfare or rights of subjects or others.

7.1.5 Serious Adverse Event

An adverse event or suspected adverse reaction is considered serious if in the view of the investigator or the sponsor, it results in any of the following:

- Death,
- A life-threatening adverse drug experience
- Inpatient hospitalization or prolongation of existing hospitalization
- Persistent or significant incapacity or substantial disruption of the ability to conduct normal life functions
- A congenital anomaly/birth defect.
- Important medical events that may not result in death, be life-threatening, or require hospitalization may be considered a serious adverse drug experience when, based upon appropriate medical judgment, they may jeopardize the patient or subject and may require medical or surgical intervention to prevent one of the outcomes listed in this definition.

7.1.6 Disability

A substantial disruption of a person's ability to conduct normal life functions.

7.1.7 Life-threatening adverse drug experience

Any adverse event or suspected adverse reaction that places the patient or subject, in the view of the investigator or sponsor, at immediate risk of death from the reaction as it occurred, i.e., it does not include a reaction that had it occurred in a more severe form, might have caused death.

7.1.8 Protocol Deviation (NIH Definition)

Any change, divergence, or departure from the IRB-approved research protocol.

7.1.9 Non-compliance (NIH Definition)

The failure to comply with applicable NIH Human Research Protections Program (HRPP) policies, IRB requirements, or regulatory requirements for the protection of human research subjects.

7.1.10 Unanticipated Problem

Any incident, experience, or outcome that:

- Is unexpected in terms of nature, severity, or frequency in relation to
 - (a) the research risks that are described in the IRB-approved research protocol and informed consent document; Investigator's Brochure or other study documents, and
 - (b) the characteristics of the subject population being studied; **AND**
- Is related or possibly related to participation in the research; **AND**

- Suggests that the research places subjects or others at a *greater risk of harm* (including physical, psychological, economic, or social harm) than was previously known or recognized.

7.2 NCI-IRB AND CLINICAL DIRECTOR (CD) REPORTING

7.2.1 NCI-IRB and NCI CD Expedited Reporting of Unanticipated Problems and Deaths

The Protocol PI will report in the NIH Problem Form to the NCI-IRB and NCI CD:

- All deaths, except deaths due to progressive disease
- All Protocol Deviations
- All Unanticipated Problems
- All non-compliance

Reports must be received within 7 days of PI awareness via iRIS.

7.2.2 NCI-IRB Requirements for PI Reporting at Continuing Review

The protocol PI will report to the NCI-IRB:

1. A summary of all protocol deviations in a tabular format to include the date the deviation occurred, a brief description of the deviation and any corrective action.
2. A summary of any instances of non-compliance
3. A tabular summary of the following adverse events:
 - All Grade 2 **unexpected** events that are possibly, probably or definitely related to the research;
 - All Grade 3 and 4 events that are possibly, probably or definitely related to the research;
 - All Grade 5 events regardless of attribution;
 - All Serious Events regardless of attribution.

NOTE: Grade 1 events are not required to be reported.

7.2.3 NCI-IRB Reporting of IND Safety Reports

Only IND Safety Reports that meet the definition of an unanticipated problem will need to be reported to the NCI IRB.

7.3 IND SPONSOR REPORTING CRITERIA

An investigator must immediately report to the sponsor, using the mandatory MedWatch form 3500a, any serious adverse event, whether or not considered drug related, including those listed in the protocol or investigator brochure and must include an assessment of whether there is a reasonable possibility that the drug caused the event.

- All Grade 5 (fatal) events (except death due to progressive disease) must be reported via email within 24 hours. A complete report must be submitted within one business day.
- All other serious adverse events including deaths due to progressive disease must be reported within one business day

Study endpoints that are serious adverse events (e.g. all-cause mortality) must be reported in accordance with the protocol unless there is evidence suggesting a causal relationship between the drug and the event (e.g. death from anaphylaxis). In that case, the investigator must immediately report the death to the sponsor.

Events will be submitted to the Center for Cancer Research (CCR) at: [contact] and to the CCR PI and study coordinator.

7.3.1 Reporting Pregnancy

7.3.1.1 Paternal exposure

Male patients should refrain from fathering a child or donating sperm during the study and for one month after the last dose of PROSTVAC. Pregnancy of the patient's partner is not considered to be an AE. However, the outcome of all pregnancies (spontaneous miscarriage, elective termination, ectopic pregnancy, normal birth, or congenital abnormality) occurring from the date of the first dose until one month after the last dose should, if possible, be followed up and documented.

7.4 SAFETY REPORTING CRITERIA TO THE PHARMACEUTICAL COLLABORATORS

All events listed below must be reported in the defined timelines to [contact].

The CCR Office of Regulatory Affairs will send all reports to the manufacturer as described below.

The Investigator should complete and submit an SAE Medwatch 3500 Form, containing all information that is required by the Regulatory Authorities, to BNIT by e-mail within 24 to 48 hours of awareness for SAEs deemed to be possibly, probably or definitely related to the study vaccines.

The SAE documentation, including the Medwatch 3500 Form and available source records, should be emailed to:

Bavarian Nordic, Inc.

Email: [contact];

Fax number for pharmacovigilance at BN: [contact]

Attention: [name]

The following minimum information is required:

- Study number/IIT regulatory identifier
- Subject number, sex and age
- The date of report
- A description of the SAE (event, seriousness of the event)
- Causal relationship to the study drug

Follow-up information for the event should be sent within 7 days as necessary.

SAEs that are deemed unrelated or unlikely to be due to the study vaccines are submitted quarterly to BNIT at the following address:

Bavarian Nordic, Inc.
Email: [contact];
Fax number for pharmacovigilance at BN: [contact]
Attention: [name]

